2.2. Study Design

This study was designed as a randomized, controlled crossover clinical trial. Each participant used both interdental cleaning methods, water flossing and regular flossing, in two separate visits with a 14-day washout period between interventions to minimize carryover effects.

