2.8. Sample Size Calculation

The sample size was calculated using G*Power software (version 3.1.9.7), based on the findings of Abdellatif et al., who compared the efficacy of water flossers and regular floss in plaque removal [13]. Assuming a power of 80%, a two-tailed significance level (α) of 0.05, and an effect size derived from the cited study, a total of 44 participants (22 per group) were required to achieve sufficient statistical power.

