2.9. Study Procedures

Participants were screened according to the inclusion and exclusion criteria. Parents were informed that participation was voluntary and that all collected data would remain confidential and accessible only to the research team.

Each participant was randomly assigned to start with one of the following:

- Group A: Unflavored, unwaxed regular dental floss (Oral-B, USA)(Figure 1a), or
- Group B: Water flosser (Waterpik Cordless Plus Water Flosser, USA)(Figure 1b).

After the first visit, a 14-day washout period was observed before the crossover intervention was applied.

At the first visit, demographic data (participant initials, age, and sex) and group allocation were recorded. A clinical examination was performed to assess the Plaque Index (PI) using the criteria of Silness and Le (1964). All participants received standardized oral hygiene instructions, including brushing twice daily with the Modified Bass Technique using a soft-bristled toothbrush and fluoridated toothpaste. Participants received instructions on the proper use of the assigned interdental cleaning method and performed the procedure independently.

The Plaque Index (PI) was recorded for all teeth according to the following criteria:

- 0: No plaque in the gingival area.
- 1: A film of plaque adhering to the free gingival margin and adjacent tooth area, detectable only by a probe.
- 2: Moderate accumulation of soft deposits visible to the naked eye within the gingival margin.
- 3: Abundant soft matter within the gingival pocket and/or along the gingival margin.

At the second visit, participants switched to the opposite cleaning method (water flosser or regular floss), and plaque scores were reassessed using the same PI criteria.

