2.10. Statistical Analysis

Descriptive statistics, including means, medians, standard deviations, interquartile ranges (IQRs), minima, and maxima, were calculated to summarize the data. Normality was assessed using the Kolmogorov-Smirnov test, and Levene's test was conducted to evaluate the assumption of equal variances. Due to the violation of the normality assumption, the Wilcoxon signed-rank test was used for the comparison of plaque scores between water floss and regular floss. This test was also used for additional paired comparisons, including before and after flossing, anterior versus posterior teeth, maxillary versus mandibular arches, and right versus left sides.

Linear regression analysis was used to assess the association between gender and plaque scores after flossing for each flossing method, with adjusted

models controlling for age and number of surfaces flossed. The significance level was set at $p\text{-value} = 0.05$. All analyses were performed using Stata version 16.1 (StataCorp, College Station, TX). (a)

(a)

(b)

Figure 1. Oral hygiene aids used in the study: (a) Regular dental floss (Oral-B, USA); (b) Water flosser (Waterpik Cordless Plus Water Flosser, USA).

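### The comparison of the two methods leaves out the same visit's pre-floss plaque score, and the visit schedule does not match the scores the analysis needs; the cost is mainly precision

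*Combined protocol and SAP*

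**What the plan says.** **Design (2.2).** "Each participant used both interdental cleaning methods, water flossing and regular flossing, in two separate visits with a 14-day washout period". Each child is therefore their own control, and section 2.5 randomises the order.

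**Scoring schedule (2.9).** At visit 1, "A clinical examination was performed to assess the Plaque Index (PI"), and this comes before the hygiene instruction, the device instruction and the flossing itself. No later scoring at that visit is explicitly timed. At visit 2, "participants switched to the opposite cleaning method (water flosser or regular floss), and plaque scores were reassessed using the same PI criteria"; whether that score precedes or follows flossing is not stated.

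**Analysis (2.10).** For the main question, "the Wilcoxon signed-rank test was used for the comparison of plaque scores between water floss and regular floss". No change score, pre-floss covariate or period term is named. Then: "This test was also used for additional paired comparisons, including before and after flossing". The same section regresses post-floss plaque on gender separately for each method, adjusting for age and number of surfaces.

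**Sample size (2.8).** With 80% power and a two-sided α of 0.05, the section concludes that "a total of 44 participants (22 per group) were required to achieve sufficient statistical power". The effect it rests on is described only by its source, and no value is given.

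**The concern.** The trial asks how much plaque one use of each method removes. A post-floss score reflects both the removal and the plaque the child arrived with that day. Starting plaque can differ between a child's two visits through ordinary daily variation, and because every child is taught a brushing technique at visit 1 and returns after 14 days. If the method comparison ignores the starting score, that variation stays in the treatment difference and widens its interval.

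The schedule adds a second difficulty. The analyses in 2.10 need four scores per child: before and after flossing, under each method. Section 2.9 clearly describes only two scoring occasions and times only the first relative to flossing. A reader cannot tell from 2.9 which score enters which comparison.

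**Working it through.** **1. Sections side by side.**

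| Score | Needed by 2.10 | Described in 2.9 |
|---|---|---|
| Visit 1, pre-floss | yes (before/after) | yes |
| Visit 1, post-floss | yes (before/after; method comparison; gender regression) | not explicitly timed |
| Visit 2, pre-floss | yes (before/after) | not explicit |
| Visit 2, post-floss | yes (as visit 1) | one reassessment, untimed |

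**2. What the plan's 44 implies.** With no effect size stated, 44 cannot be reproduced, only back-solved (two-sided α 0.05, 80% power, noncentral t).
- Paired, 44 pairs: standardised mean difference dz = 0.432.
- Two independent groups of 22: d ≈ 0.865.

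The plan does not say which was used. The phrase giving 22 per group fits the second.

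**3. Variance removed.** Let r be the correlation, across children, between the within-child difference (water minus regular) in pre-floss PI and that in post-floss PI. The adjusted variance is (1 − r²) times the unadjusted variance. So dz becomes dz/√(1 − r²), and the interval narrows by 1 − √(1 − r²). The plan gives no r; 0.3 to 0.7 is assumed.

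**4. Power if 44 was a paired calculation (dz = 0.432).**

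| r | variance removed | interval narrower by | adjusted dz | power |
|---|---|---|---|---|
| 0 | 0% | 0% | 0.432 | 80.0% |
| 0.3 | 9% | 4.6% | 0.453 | 83.6% |
| 0.5 | 25% | 13.4% | 0.499 | 89.9% |
| 0.7 | 49% | 28.6% | 0.605 | 97.5% |

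Taking one degree of freedom off for the covariate (42 instead of 43) changes each figure by less than 0.1 point; at r = 0 power goes from 80.0% to 79.96%.

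**5. Power if 44 was two groups of 22 (d ≈ 0.865).** Assume equal SDs and no correlation between a child's two scores. Then dz = 0.865/√2 = 0.612, and 44 pairs already give about 98% power unadjusted. Positive correlation raises it further. Adjustment can add at most about 2 points, although the interval narrows by the same proportions as in step 4.

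**6. Change score as an alternative.** With equal pre- and post-floss variances, its variance relative to post-floss alone is 2(1 − r): 1.4 at r = 0.3, 1.0 at 0.5, 0.6 at 0.7. From dz = 0.432, power is 65.8%, 80.0% and 95.1%. It helps only when r exceeds 0.5.

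**7. When bias appears.** Suppose starting plaque shifts by δ at visit 2 and the sequences hold nA and nB children. The unadjusted post-floss difference is then off by r × δ × (nA − nB)/(nA + nB), again with equal pre- and post-floss variances.
- 22/22: zero, whatever δ is. Simulation (2,000 runs, r = 0.7) agrees: mean error about 0 even at δ = 1 SD.
- 26/18, δ = 1 SD, r = 0.7: 0.7 × 1 × 8/44 = 0.13 within-child SD of a single score; simulation gives the same size. A plain change score is off by (1 − 0.7) × 8/44 ≈ 0.05 in the other direction (simulated 0.06), so a period term is needed in either case.
- Section 2.5 does not mention blocking. If allocation were simple, a gap of 8 or more among 44 children has probability 0.29.

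**The case against.** **The post-floss scores exist.** A reader of 2.9 alone might infer that the first method has no post-floss score and the second no pre-floss score, so that the method comparison mixes the two. The documents do not support that. Section 2.10 analyses post-floss plaque under each method and tests before against after. In 2.9, the statement that PI was recorded for all teeth follows the flossing step and may refer to a post-floss scoring. The schedule is inconsistently described; missing data are not shown. This objection stands.

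**Randomised order protects against bias.** A reader might also infer that any visit-to-visit difference in starting plaque is misread as a method effect. With balanced sequences a common shift cancels (step 7), so the brushing instruction alone does not bias the comparison. This stands too: without carryover, bias needs a shift together with imbalance.

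**The term 'plaque scores' might mean change.** Possibly, but 2.10 does not say so and lists before/after as an additional comparison. The endpoint still needs stating, and a change score would not be the best use of the pre-floss data at low r.

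**The power gain may be small.** Correct if 44 came from an independent-groups calculation (step 5). The range must be shown whole.

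**The gender regressions also omit pre-floss plaque.** They ask a different question, and a gender difference could run through starting plaque. They are not at fault here.

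**Conclusion.** The concern holds as a loss of precision and an inconsistency between sections. As written, the main comparison does not use a pre-floss score that another analysis in the same section requires, and 2.9 does not set out the scores that 2.10 analyses. It is not evidence that scores were never taken or that the treatment comparison is biased.

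The size depends on two things the plan does not give: r, and whether 44 was a paired or a two-group calculation. Over r = 0.3 to 0.7 the gain is about 4 to 17.5 points of power on the paired reading and at most about 2 points on the other. The interval is 5% to 29% narrower on either. These are t-based approximations to a rank analysis. The downside is about one degree of freedom if r is near 0.

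**What to change.** **Section 2.9.** State that PI is scored immediately before and immediately after flossing at both visits.

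**Section 2.10.**
- Name post-floss PI as the outcome of the method comparison.
- Regress the within-child difference in post-floss PI (water minus regular) on the within-child difference in pre-floss PI, with a sequence term coded +1/−1 to absorb period. The intercept is the method effect.
- Because normality was judged violated, use a rank-based or permutation version, or robust standard errors.
- Keep the Wilcoxon test as a sensitivity analysis.
- Leave the gender regressions unchanged.

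**Cost.** Wording and one model. The before/after analysis already requires the pre-floss scores, so no new type of measurement is involved. Section 2.3 describes data collection in the past tense, ending in April 2025. If it is complete, rewriting 2.9 cannot create scores: report when each PI was actually taken and apply the adjusted analysis to the pre-floss scores already recorded, labelled as specified after data collection.

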2.10. Statistical Analysis

Descriptive statistics, including means, medians, standard deviations, interquartile ranges (IQRs), minima, and maxima, were calculated to summarize the data. Normality was assessed using the Kolmogorov-Smirnov test, and Levene's test was conducted to evaluate the assumption of equal variances. Due to the violation of the normality assumption, the Wilcoxon signed-rank test was used for the comparison of plaque scores between water floss and regular floss. This test was also used for additional paired comparisons, including before and after flossing, anterior versus posterior teeth, maxillary versus mandibular arches, and right versus left sides.

Linear regression analysis was used to assess the association between gender and plaque scores after flossing for each flossing method, with adjusted

models controlling for age and number of surfaces flossed. The significance level was set at $p\text{-value} = 0.05$. All analyses were performed using Stata version 16.1 (StataCorp, College Station, TX). (a)

(a)

(b)

Figure 1. Oral hygiene aids used in the study: (a) Regular dental floss (Oral-B, USA); (b) Water flosser (Waterpik Cordless Plus Water Flosser, USA).

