2.5.2. Allocation Concealment

Each allocation code was printed, cut into identical slips, and sealed in opaque envelopes. The envelopes were placed in a single container. Upon recruitment, each participant selected one envelope to determine their assigned intervention sequence.

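### The main comparison of water flosser and string floss makes no allowance for a period effect, although the trial randomises order and first-visit instruction makes such an effect plausible

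*Combined protocol and SAP*

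**What the plan says.** Section 2.2 describes a crossover in which each child uses both methods at separate visits, "with a 14-day washout period between interventions to minimize carryover effects". Sections 2.5.1 and 2.5.2 make order the randomised factor: "each participant selected one envelope to determine their assigned intervention sequence". They state neither blocking nor how many envelopes of each kind were in the container. Section 2.8 gives "a total of 44 participants (22 per group) were required to achieve sufficient statistical power".

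Among the first-visit procedures, section 2.9 says: "All participants received standardized oral hygiene instructions, including brushing twice daily". Children are also taught the assigned method. Plaque is scored again at the second visit, after the switch.

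For the main comparison, section 2.10 says: "the Wilcoxon signed-rank test was used for the comparison of plaque scores between water floss and regular floss". The plan has no period term, sequence term or order-stratified test. The only adjusted model is the gender regression, which is fitted for each method with age and number of surfaces flossed as covariates.

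**The concern.** Instruction meant to lower plaque is described at visit 1, and the second plaque assessment comes 14 days later. Plaque at visit 2 may therefore differ from visit 1 whichever method is used. The washout is aimed at carryover of the first method; it is not a way of undoing learned brushing.

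A shift of this kind enters the water-minus-string difference with one sign in children who start with string and the opposite sign in those who start with water. The signed-rank test does not know which child is which. With equal orders the shift cancels from the average but adds spread, and power is lost. With unequal orders part of it stays in the estimate. This is the trial's central comparison, and the variable needed to remove the shift is already recorded at visit 1 as group allocation.

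**Working it through.** **The plan's own figure.** Section 2.8 uses "a two-tailed significance level (α) of 0.05", 80% power and "an effect size derived from the cited study". No number is given for that effect size, so 44 cannot be reproduced. Solving backwards for 80% power:

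- paired t-test, N = 44: standardised within-child effect 0.432;
- signed-rank test, N = 44, relative efficiency 3/3.1416 = 0.955: 0.443;
- two-sample t-test, 22 per group: d = 0.865.

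The wording in 2.8 does not say which type of calculation was used, so both ends are carried forward.

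**Model.** Let D be water minus string within a child, with SD 1; τ the method effect; and δ the shift from visit 1 to visit 2 in units of that SD (assumed, 0 to 1.0). Then:

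- string first: mean D = τ + δ;
- water first: mean D = τ − δ.

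Pooled over N children, the mean of D is off by δ × (n string-first − n water-first)/N. With equal orders this is zero, but the pooled variance of D becomes 1 + δ².

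**Equal orders (22/22).** With no method effect, the large-sample rejection rate is 2Φ(−1.96 × √(1 + δ²)):

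- δ = 0.5: 1.96 × √1.25 = 2.19, giving 2.8%;
- δ = 1.0: 1.96 × √2 = 2.77, giving 0.6%.

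Simulation (20,000 trials per setting, normal errors) gives about 2.8% and 0.5%, against about 5% for a rank-sum test of period differences between orders. Simulated power at τ = 0.443:

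| Shift δ | Signed-rank | Period-adjusted rank-sum |
|---|---|---|
| 0 | about 80% | about 80% |
| 0.25 | about 79% | about 80% |
| 0.5 | about 72% | about 80% |
| 1.0 | about 47% | about 80% |

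At τ = 0.865, signed-rank power is at least 99% even at δ = 1.0.

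**Unequal orders, δ = 0.5.**

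- 18/26: bias = 0.5 × 8/44 = 0.09 SD.
- 16/28: bias = 0.5 × 12/44 = 0.14 SD.

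Type I error given a 16/28 split:

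- pooled variance = 1 + 0.25 × (1 − (12/44)²) = 1.231;
- rejection threshold = 1.96 × √1.231 = 2.17;
- bias in standard errors = 0.136 × √44 = 0.90;
- P(Z > 1.27) + P(Z < −3.08) = about 10%.

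Simulation agrees (about 10%). The same steps at 18/26 give about 6%, and so does simulation. The period-adjusted test stays near 5% in both.

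**How likely is an uneven split?** If the 44 draws were independent and 1:1, a split of 18/26 or worse has binomial probability 29%, and 16/28 or worse about 10%. Averaged over such draws, the signed-rank test's type I error is about 5% at every shift from 0 to 1.0. If 22/22 were achieved and six children, all from one order, then missed visit 2 (16/22), type I error is about 3.5% to 5%; the bias at δ = 0.5 would be 0.5 × 6/38 = 0.08 SD.

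**The case against.** A reader might infer that the envelope draws or missed second visits push the trial's false-positive rate above 5%. The documents do not support that. Under independent 1:1 draws the sign of the shift is itself randomised, so the signed-rank test keeps its level on average. Losses from a planned 22/22 do not raise the level in the case examined. Material inflation appears only conditional on a large achieved imbalance, and no document reports one.

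The size of the power loss is also open to challenge. The 47% figure needs a shift of 1.0 SD, more than twice the assumed method effect; at 0.25 SD the loss is a point or two. If the sample size came from a two-sample calculation with d = 0.865, the paired effect would be 0.865/√(2 × (1 − r)) for within-child correlation r. That is 0.61 at r = 0 and 0.865 at r = 0.5. Signed-rank power is then about 95% at 0.61 with a 0.5 SD shift, and at least 99% at 0.865.

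Section 2.10 does not say whether post-flossing scores or before-after changes are compared between methods. Using changes would shrink the shift, though it need not remove it.

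It would also be too strong to say that ignoring sequence is an error in itself. A sequence main effect cancels within a child; sequence is needed only to take out period. Nor is the plan without summaries of the effect, since it provides means and medians. What it lacks is a confidence interval for the paired difference.

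All of this stands as a limit on size. None of it gives the plan a way to detect or remove a period effect.

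**Conclusion.** The point holds as a should-fix matter of efficiency, with a bias risk that depends on the achieved split. With 22 per order the planned test is valid and unbiased but conservative. If the paired effect is about 0.44 SD, it costs about 1, 8 and 33 points of power at shifts of 0.25, 0.5 and 1.0 SD; if the effect is about 0.87 SD, it costs almost nothing. With unequal orders the estimate is off by the shift times the proportional imbalance: 0.09 SD at 18/26 and 0.14 SD at 16/28 for a 0.5 SD shift. Type I error is materially raised only given a large imbalance, to about 10% at 16/28 with that shift.

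These figures rest on normal within-child differences, an assumed shift, and an effect back-solved from the sample size. That a period effect is plausible follows from section 2.9; its existence and size are not documented. The documents do not show that the trial's result is wrong or that its overall error rate is inflated.

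**What to change.** In section 2.10, make the main comparison a rank-sum test of within-child period differences (visit 1 minus visit 2) between the two order groups. Give a Hodges-Lehmann estimate of the method effect, which is half the shift between the orders, with a 95% CI. This keeps the rank-based approach that the plan chose because of non-normality. An alternative is a mixed model with method, period and sequence and a random effect for child. It can use children seen at only one visit, which the rank-sum test cannot, but it relies on a model for the errors.

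State whether post-flossing scores or before-after changes are compared. Report the number of children randomised to, and completing, each order. Keep the signed-rank test as a sensitivity analysis.

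The cost is a revised paragraph and a few lines of Stata code. Because allocation and visit are recorded, it can be applied to data already collected. With equal orders and no period effect, about 1 point of power or less is lost; at 16/28 the loss is up to about 4 points.

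### The secondary gender regressions omit pre-floss plaque and contain no gender-by-method test, so they cannot support statements about plaque removal by sex or about sex differences between devices

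*Combined protocol and SAP*

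**What the plan says.** All of the gender analysis is in section 2.10 (Statistical Analysis): "Linear regression analysis was used to assess the association between gender and plaque scores after flossing for each flossing method". The adjusted versions are "models controlling for age and number of surfaces flossed". Pre-floss plaque, visit, intervention order and a gender-by-method term are not mentioned.

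Three other statements bear on the point:

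- Pre-floss scores exist, because section 2.10 also plans "additional paired comparisons, including before and after flossing".
- The design is within-child. Section 2.2 says: "Each participant used both interdental cleaning methods, water flossing and regular flossing, in two separate visits".
- Sex is an observed characteristic. Section 2.9 lists it among the first-visit items: "demographic data (participant initials, age, and sex) and group allocation were recorded".

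The method comparison is a separate analysis in which gender plays no part: "the Wilcoxon signed-rank test was used for the comparison of plaque scores between water floss and regular floss".

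**The concern.** Randomisation in this trial decides the order of the two methods. It does nothing to balance boys against girls, and recruitment is by convenience (section 2.4). If one sex arrives with more plaque, part of that excess will remain after flossing with either device. A model of the post-floss score without the pre-floss score then attributes this excess to gender. Age and a surface count do not stand in for it.

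The second problem is the split by method. With one model per device, the natural reading is to compare the two p-values and note that gender mattered for one device and not for the other. That comparison does not test whether the gender effect differs between devices, and it ignores that the same children supply both sets of scores.

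What is at stake is a secondary conclusion. A report could suggest that a device cleans better in one sex when the sexes differed only on arrival, or that the devices differ in this respect when they do not.

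**Working it through.** **Design figure in the plan.** The only one is the sample size in section 2.8: 44 children, 22 per group, from "Assuming a power of 80%, a two-tailed significance level (α) of 0.05, and an effect size derived from the cited study". No numerical effect size is given, so the 44 cannot be reproduced, and it was not set for the gender models. The point does not depend on it.

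**Inputs.** From the documents: 44 children, two-sided 0.05, post-floss plaque as outcome, no pre-floss term. Assumed, because the documents give no plaque means, SDs, correlations or sex split: 22 boys and 22 girls (not the 22 per group of section 2.8), arrival gap 0.2 PI units, within-sex pre-floss SD 0.35, pre-to-post slope 0.7, and no gender effect on removal. The residual SD is unknown and is varied.

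**Step 1: what passes through.** The gender coefficient in a post-only model has expectation slope × gap = 0.7 × 0.2 = 0.14, although removal is unaffected by gender. The within-sex SD of the post score is √((0.7 × 0.35)² + residual SD²) = √(0.0600 + residual SD²). The standardised difference is d = 0.14 / that SD. With 22 per sex, the noncentrality of the t-test on 42 degrees of freedom is d × √(22/2).

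| Residual SD | Post SD | d | Noncentrality | p<0.05, post-only model (simulated) | p<0.05, pre-floss PI added (simulated) |
|---|---|---|---|---|---|
| 0.10 | 0.265 | 0.53 | 1.76 | 41% | 5.3% |
| 0.15 | 0.287 | 0.49 | 1.62 | 35% | 5.0% |
| 0.25 | 0.350 | 0.40 | 1.33 | 26% | 5.0% |
| 0.35 | 0.427 | 0.33 | 1.09 | 19% | 4.7% |

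The simulated rates come from 4,000 trials per row. The noncentral t gives 40%, 35%, 25% and 19% for the same rows, which agrees.

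**Step 2: other gaps.** Halving the gap to 0.1 gives about 12% at residual SD 0.15 and 7% at 0.50. A second simulation worked in SD units, with age and a surface count in the model as planned (4,000 trials per scenario, pre/post correlation 0.3 to 0.9):

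| Arrival gap | p<0.05 for gender, planned model |
|---|---|
| 0 | about 5% |
| 0.3 SD | 5.5% to 12.5% |
| 0.5 SD | 7.9% to 30.1% |
| 0.8 SD | 11.4% to 61.4% |

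With pre-floss plaque added, the rate was 4.3% to 5.5% in every scenario, and the mean gender coefficient was about 0.

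**Step 3: two separate models.** The same simulation had no gender-by-method effect, the same pre-to-post relation for both methods, and a between-visit correlation of pre-floss scores of 0.7 (assumed). One method was significant and the other not in 8.1% to 9.6% of trials with no arrival gap, and in 14.1% to 28.4% with a gap of 0.5 SD. Regressing the within-child difference between methods on gender rejected in 4.1% to 5.5% across all scenarios.

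**Step 4: period.** Each per-method model mixes first-visit and second-visit scores. Because order is randomised, visit is independent of sex in expectation. Simulating period effects of 0, 0.2 and 0.4 (SD 0.35) left the mean bias in the gender coefficient at about 0 and rejection at about 5.3%. Leaving period out costs precision and does not bias this coefficient.

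**The case against.** The strongest reply is that the plan promises only an association between gender and plaque after flossing. For that question, a gap present on arrival is part of the answer, and a significant coefficient detects a real difference in post-floss plaque. This stands: the percentages above are error rates only if the coefficient is read as an effect on removal. The plan also nowhere says that effect modification will be tested.

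Three stronger readings are tempting, and the documents do not support them.

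- A reader might infer that the gender results are wrong or must be biased. No figure in the documents shows a sex gap on arrival, and without one there is no bias.
- A reader might infer that the surface count is a result of the child's flossing, so that adjusting for it removes part of a real gender difference. The plan does not define the count. It may be the surfaces available, fixed by the dentition before flossing.
- A reader might infer that ignoring period distorts the gender coefficient. With randomised order it does not, in expectation.

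What remains is that the models are run per device in a trial whose purpose is to compare devices. Readers will therefore be drawn to the removal and between-device readings, which these models cannot support.

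**Conclusion.** The point holds as an improvement to a secondary analysis. It is not an error in the main comparison, which does not involve gender and is unaffected.

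Read as a gender effect on removal, the planned models can be confounded by plaque on arrival. With a gap of 0.2, SD 0.35, slope 0.7 and 22 children per sex, gender reaches p<0.05 in about 19% to 41% of trials for residual SDs of 0.35 to 0.10, against about 5% with pre-floss PI in the model. Every one of these inputs is an assumption. No single figure in the range should be quoted as the size of the problem.

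The lack of a test across methods follows from the text alone and needs no assumption.

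**What to change.** - Add the same-visit pre-floss PI to each gender model. Keep the association without it, labelled as descriptive.
- Base any statement that gender effects differ by method on a gender-by-method estimate with its 95% CI. Either regress the within-child method difference on gender, or fit a mixed model to both visits with gender, method, their interaction, period and sequence, and a random effect for child. Period is there for precision. Label the result exploratory.
- Define the number of surfaces flossed. Use it as a covariate only if it counts the surfaces available before flossing. Section 2.7 sets a minimum number of posterior contacts, but nothing shows that a count at screening was stored, so it should not be assumed available as a substitute.

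The cost is analysis-plan wording and code, with no new children or visits. One condition should be confirmed: section 2.9 describes the second visit only as a reassessment of plaque, so the plan should state that a pre-floss score was taken at both visits, as the before-and-after comparison in section 2.10 implies.
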